4.3 JUSTIFICATION FOR DOSE

The dose of 300 mg daily was selected because this was the most efficacious dose for TG reduction in adults. The drug is oral, once a day based on the previous studies. Most children in this study will be >70 kg. A minimum weight of 60 kg will be set to eliminate children receiving a higher dose/kg than intended.

4.4 END OF STUDY DEFINITION

A participant is considered to have completed the study if he or she has completed all phases of the study through week 12. The end of the study is defined as completion of the last visit or procedure shown in the SoA in the trial for all enrolled participants.

5 STUDY POPULATION

5.1 INCLUSION CRITERIA

In order to be eligible to participate in this study, an individual must meet all of the following criteria:

1. Provision of signed and dated informed consent form
2. Provision of signed and dated assent, if indicated
3. Stated willingness to comply with all study procedures and availability for the duration of the study
4. Children aged 12-17 years at the time of informed consent
5. History of clinical diagnosis of NAFLD including a, b and c below:
 - a. Medical history eliminating, other chronic liver diseases (for example mitochondrial diseases, hepatotoxic drugs, anorexia nervosa)
 - b. Laboratory studies: negative testing for hepatitis C and normal ceruloplasmin
 - c. Either liver biopsy confirming NAFLD or MRI $> 10\%$ steatosis within the past three years
6. ALT ≥ 54 U/L for boys or ≥ 46 U/L for girls and ≤ 250 U/L at screening visit and within past three months (prior to screening). If ALT at screening is more than two times the historic value (or a historic value is not available), the subject will be asked to repeat the ALT after four weeks. If

the repeat ALT is more than 50% increased or decreased over the screening ALT a third ALT may be obtained. If a third ALT is not within 50% of the previous value then the subject is ineligible, but may be rescreened at a later date.

7. Body weight \geq 60 kg at the time of screening
8. Able to take oral medication and be willing to adhere to the GEM-IIT-601 regimen
9. Minimum of three months of attempted lifestyle modification to treat the NAFLD and agreement to adhere to Lifestyle Considerations (see section 5.3) throughout study duration

5.2 EXCLUSION CRITERIA

An individual who meets any of the following criteria will be excluded from participation in this study:

1. Heart disease (e.g., myocardial infarction, heart failure, unstable arrhythmias)
2. Seizure disorder
3. Active coagulopathy (INR $>$ 1.4)
4. Renal dysfunction with an estimated glomerular filtration rate (eGFR) $<$ 60ml/min/1.73 calculated using Schwartz Bedside GFR calculator for children
5. History of active malignant disease requiring chemotherapy or radiation
6. History of significant alcohol intake (AUDIT questionnaire) or inability to quantify alcohol consumption
7. Use of new medications or supplements with the intent to treat NAFLD/NASH during the 30 days prior to screening, including statin therapy. Medications or supplements (including metformin and vitamin E) that they have been on and are on a stable dose are acceptable
8. History of bariatric surgery or planning to undergo bariatric surgery during study duration
9. Clinically significant depression
10. Any girl nursing, planning a pregnancy, known or suspected to be pregnant, or who has a positive pregnancy screen
11. Non-compensated liver disease defined as cirrhosis and any one of the following hematologic, biochemical, and serological criteria on entry into protocol:
 - Hemoglobin $<$ 10 g/dL;
 - White blood cell (WBC) $<$ 3,500 cells/mm³;
 - Neutrophil count $<$ 1,500 cells/mm³;
 - Platelets $<$ 150,000 cells/mm³;
 - Total bilirubin $>$ 1.3 mg/dL unless due to Gilbert's syndrome (subjects with a history of Gilbert's syndrome may be included if both direct bilirubin and the reticulocyte count do not exceed the ULN [reflexive direct bilirubin testing will be used to confirm Gilbert's syndrome])
 - Albumin $<$ 3.2 g/dL
 - International normalized ratio (INR) $>$ 1.3
 - Abnormal alkaline phosphatase
 - Any history of ascites, variceal bleeding, hepatic encephalopathy, or hepatocellular carcinoma (HCC)
12. Poorly controlled diabetes mellitus (hemoglobin A1c (HbA1c) $>$ 8%) or requiring insulin
13. Patients with type I diabetes mellitus
14. Chronic liver disease other than NAFLD
15. Patients on CYP 3A4 inhibitors such as itraconazole or macrolide antibiotics are excluded
16. Patients who are on thiazolidinediones, fibrates or fish oils are excluded

17. Patients who are on daily prescription medications are excluded except for allergy medications, ADHD medications, asthma medications, or any other acceptable medication in the opinion of the investigator
18. Abnormal creatinine kinase levels at screening (may be repeated if the elevation is thought to be exercise related)
19. Sexually active female participants of childbearing potential and Tanner stage ≥ 4 or menstruating unwilling to utilize two acceptable forms of contraception from screening through completion of the study or unwilling to complete pregnancy tests throughout the study
20. Currently enrolled in a clinical trial or who received an investigational study drug within 90 days of screening
21. Participants who are not able or willing to comply with the protocol or have any other condition that would impede compliance or hinder completion of the study, in the opinion of the investigator

5.3 LIFESTYLE CONSIDERATIONS

All participants will be required to have attempted lifestyle changes as a treatment for their NAFLD. This will include attempting a dietary improvement and physical activity. Because of the highly variable success with this, no specific requirement for weight loss will be set.

Within the trial, all children will be given standardized lifestyle-based treatment at the Baseline visit. These will consist of the American Heart Association recommended healthy eating pattern for children (http://www.heart.org/HEARTORG/HealthyLiving/Dietary-Recommendations-for-Healthy-Children_UCM_303886_Article.jsp#.WZx7NOMQwaY).

It is important that participants are instructed to not undertake any form of strenuous physical activity for at least 24 hours prior to blood testing.

All clinic visit assessments except screening require the children to fast overnight. This is defined as no food or caloric beverages for a minimum of eight hours prior to sample collection. They will be permitted to have water and it will be encouraged in the evening and in the morning before the visit to promote good hydration.

5.4 SCREEN FAILURES

Screen failures are defined as participants who consent to participate in the clinical trial but are not subsequently entered in the study. A minimal set of screen failure information is required to ensure transparent reporting of screen failure participants, to meet the Consolidated Standards of Reporting Trials (CONSORT) publishing requirements and to respond to queries from regulatory authorities. Minimal information includes demography, screen failure details, eligibility criteria, and any serious adverse event (SAE).

Individuals who do not meet the criteria for participation in this trial (screen failure) because of a low ALT, body weight too low, other medication use or failure to meet inclusion or do meet exclusion criteria may be rescreened if in the view of the investigator there is a high likelihood that they would qualify on the rescreening. Rescreened participants will get the same screening number.

5.5 STRATEGIES FOR RECRUITMENT AND RETENTION

- The target study sample size is 36 completed participants and it is expected that there will be a 33% screen fail rate and a 10% drop out rate. This will require screening approximately 60 individuals, with 40 enrolled. This will allow the study to reach the target completion of 36 participants.
- Anticipated accrual rate = 2-3 participants per site per month
- Anticipated number of sites – 3 sites
- Source of participants – Well-qualified research sites with documented expertise working with this subject population
- Potential patients will be located by chart review to look for eligibility criteria or referral by the treating physician or by reviewing lists of patients who have indicated interest in NAFLD studies
- Participant retention will be enhanced by providing age appropriate activities during the visit (movies, video games, puzzles etc.), by providing transportation assistance, by reminder phone calls and through compensation for time and travel to study visits.
- Participants will receive compensation for study participation and for transportation costs. Compensation will be based on visit length and will be dispensed to the parent/legal guardian.

6 STUDY INTERVENTION

6.1 STUDY INTERVENTION(S) ADMINISTRATION

6.1.1 STUDY INTERVENTION DESCRIPTION

[REDACTED]

USAN Name: Gemcabene calcium

Parent Compound: [REDACTED]

USAN Name: Gemcabene

CAS Registry number: [REDACTED]

Molecular Formula

[REDACTED]

Relative Molecular Mass

[REDACTED]

Manufacturer (drug substance): [REDACTED]

Gemcabene Tablets

[REDACTED]

Primary Packaging

[REDACTED]

6.1.2 DOSING AND ADMINISTRATION

The dose is 300 mg orally once a day.

The first dose of study drug will be administered at the research site on Study Day 1. On days with a scheduled office visit with blood sample collection, subject will remain fasted and should not take gemcabene until after the blood samples are collected at the site. On all other days, the subject will self-dose: taking study drug at the same time in the morning with a full glass (8 ounces) of water either with or without food. If a subject misses a dose prior to 6:00 PM, then the subject should take their dose. However, if past 6:00 PM, the subject should not dose and then count the dose as a “missed dose.” The subject will resume normal dosing the next day (i.e., do not take two doses the following day).

6.2 PREPARATION/HANDLING/STORAGE/ACCOUNTABILITY

6.2.1 ACQUISITION AND ACCOUNTABILITY

The IP will be dispensed to each site at study initiation. IP will be monitored and stored by the research pharmacy at each site. The research pharmacist will dispense to the study participants or study investigator at Baseline and at Week 6. At the end of the study, expired or unused product will be destroyed.

6.2.2 FORMULATION, APPEARANCE, PACKAGING, AND LABELING

[REDACTED]

Study drug will be prepared in bottles with 30 days of dosing contained within each bottle. The subjects will be asked to take one tablet per day. A 6-week supply (two bottles) will be dispensed at Baseline

and at the Week 6 visit. This will include an extra 2 weeks of additional drug as a backup supply to account for visit windows.

6.2.3 PRODUCT STORAGE AND STABILITY

The study drug will be stored at controlled room temperature (15 to 30°C) in a secured location (locked) with access restricted to authorized personnel only. Storage temperature will be monitored and recorded.

Upon receipt of study drug, the Investigator or designee will conduct a complete inventory of all study drug and ensure no damage occurred during shipment.

The Investigator will maintain adequate records documenting the receipt, use, loss, or other disposition of study drug. Drug accountability logs will identify the study drug code number and account for the disposition on a subject-by-subject basis, including specific dates and quantities. The drug accountability logs will be signed by the individual who dispenses the study drug and copies will be provided to the Sponsor.

6.2.4 PREPARATION

No preparation is necessary.

6.3 MEASURES TO MINIMIZE BIAS: RANDOMIZATION AND BLINDING

This is an open label, unblinded early phase study so there are no measures for blinding.

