3 ENDPOINTS

Primary Endpoint:

- Percent change in ALT from Baseline to Week 12

Secondary Endpoints:

- Absolute change in ALT from Baseline to Weeks 6 and 12
- Percent change in ALT from Baseline to Week 6 and the mean of Week 6 and Week 12
- Absolute change and percent change in hepatic steatosis from Baseline to Week 12 as measured by MRI (volumetric fat fraction-hepafat)
- Absolute change and percent change in pancreatic fat from Baseline to Week 12 as measured by MRI (HepaFat)
- Absolute change and percent change in AST from Baseline to Week 6 and Week 12
- Absolute change and percent change in insulin sensitivity as assessed by fasting insulin, fasting glucose, and HOMA-IR from Baseline to Week 6 and Week 12
- Absolute change and percent change in GGT from Baseline to Week 6 and Week 12
- Absolute change and percent change in serum lipids including total cholesterol, non-HDL-C, HDL-C, VLDL-C, LDL-C, and triglycerides (TG) from Baseline to Week 6 and Week 12
- Absolute change and percent change in apolipoproteins including apoA-1, apoB, apoC-II, apoE and apoCIII
- Absolute change and percent change in inflammatory markers such as hsCRP, IL-1B, IL-6 and procollagen III.
- Absolute change and percent change in lipoprotein particle sizes (VLDL, HDL, LDL, chylomicrons [NMR])
- Absolute change and percent change in post-prandial lipids (total cholesterol, non-HDL-C, HDL-C, VLDL-C, LDL-C, TG, lipoprotein particle size)
- Absolute change and percent change in rate of de novo lipogenesis using stable isotope tracers
- Change in body composition measures by AMRA from Baseline to Week 12
- Absolute change and percent change in liver inflammation and fibrosis (LIF and cT1) scores by MRI (Liver MultiScan).
- Absolute change and percent change in anthropometric measures including height, weight, body mass index, and waist circumference from Baseline to Week 12

- Safety related endpoints including adverse events (AEs), vital signs, clinical labs, hematology and urinalysis
 - Treatment tolerance and compliance
-

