ALT and hepatic steatosis have been selected as the two non-invasive biomarkers of response of NAFLD to gemcabene because they are non-invasive and are generally accepted as representing improvement in liver histology, which has been linked to clinical outcomes^{35,36}. Importantly, both ALT and hepatic steatosis are related to NAFLD biology and are sensitive to change.

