8 STUDY ASSESSMENTS AND PROCEDURES

8.1 EFFICACY ASSESSMENTS

Study Procedures:

Central Lab Tests

The primary and secondary outcomes listed below will be batched and measured at a central lab. At each indicated study visit (see SOA), plasma will be collected, aliquotted and frozen within 2 hours of collection and shipped to the Cardiovascular Research Lab at the Atlanta VA. After all study visits are completed and samples are obtained for all participants, the following tests will be measured:

- Lipid panel (TG, CHOL, HDLc, LDLc)
- Apolipoprotein panel (apoA-1, apoB, apoC-II, apoC-III, apoE)
- hsCRP
- Liver function panel (AST, ALT)
- Diabetes panel (GLU, INS, NEFA)
- Pharmacokinetics (Week 2, Week 6, Week 12 and in sub-study participants at Emory 0, 2, 4 and 6 hour)

Local (safety) labs

In order to assure the safety of participants at the time of their participation in the study, the labs listed below will be performed locally at the time of the visits and reviewed by the study staff. For those labs that are measured by the local lab and by the central lab (ALT, AST, Glu, Lipids) the central lab measurements will be used for outcome analysis. In the case that a central lab is missing, this will be noted and if the local lab is available it will be used. (also see SOA).

- CMP (includes Glu, BUN, Creatinine, Lytes, Calcium, Total Protein, Albumin, Alk Phos, AST, ALT, Total Bilirubin)
- CBC (includes WBC, RBC, HGB, HCT, MCV, MCH, MCHC, RDW, PLT)
- GGT
- CPK
- Lipid profile (includes cholesterol, triglycerides, HDL, LDL, and VLDL)
- HbA1c
- UA (includes chemical analysis, blood, nitrites, leukocyte esterase, protein)
- PT/INR

Imaging:

Limited MRI (no contrast) of the abdomen to measure percent hepatic steatosis and the liver multiscan. The Resonance Health (HepaFat) scan will be used for liver fat and pancreatic fat and the Perspectum Liver Multiscan (LIF and cT1 scores) will be used for inflammation and fibrosis. Body composition will be assessed by AMRA Medical AB (AMRA).

Patient reported outcomes:

PROMIS questionnaires fatigue, anxiety and depression (see Appendix B)

Study Procedures by Visit:

Please refer to Section 1.3 Schedule of Activities for additional visit details

Unscheduled Visits:

- Repeat MRI or labs
- Rescreening Visit
- Repeat ALT (for screening)
- Early Termination Visit

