8.2 SAFETY AND OTHER ASSESSMENTS

Specific Safety Measures:

Hemoglobin decrease

For a hemoglobin decrease of > 1.5 g/dL from baseline during the study, repeat hematology studies and reflexive evaluation of reticulocyte count will be performed. The subject's past medical history, concomitant medications (including over the counter drugs and herbal supplements), and any recent symptoms (e.g., bleeding, shortness of breath, fatigue) will be reviewed to determine a potential etiology and make a clinical assessment of the significance of the finding.

Creatinine increase

If, at any visit, a creatinine increase of > 0.3 mg/dL (27 µmol/L) from baseline, a GFR decrease of >15 mL/min from baseline is observed, a repeat chemistry/urinalysis will be performed within seven days. The subject's past medical history, concomitant medications (including over the counter drugs and herbal supplements), and any recent symptoms (e.g., fatigue, malaise, polyuria/oliguria, or palpitations) will be reviewed to determine a potential etiology and make a clinical assessment of the significance of the finding.

Possible muscle and liver injury

For muscle injury, CPK, hepatic, and renal function laboratory data will be integrated with myopathy signs and symptoms.

For liver injury, laboratory data will be integrated with hepatic signs and symptoms. Alanine aminotransferase increases > 2 × baseline with symptoms of hepatitis or > 3 × baseline with or without symptoms of hepatitis will be evaluated and managed according to guidelines for studies in patients with pre-existing liver disease. This includes a repeat assessment as soon as possible to confirm the findings and a clinical evaluation. If the participant has signs or symptoms of hepatitis or ALT > 5x baseline, the study drug will be temporarily discontinued.

Data to be provided to the participants – At a minimum, the locally run clinical labs and MRI liver fat result from baseline will be provided to each patient at the end of the study and reviewed with them by a study investigator. This includes the CMP, CBC, GGT, hemoglobin A1c, insulin, glucose and fasting lipids. The investigator may choose to share other locally run clinical labs from other time points with the participant.

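### Open-label dosing is given as the reason for no blinding at all, yet the off-site MRI analysts could be masked to visit, which in this one-arm trial means masked to treatment

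*Combined protocol and SAP*

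**What the plan says.** Section 6.3, the section on measures to minimize bias, consists of one sentence: "This is an open label, unblinded early phase study so there are no measures for blinding".

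Section 8.1 names three external imaging analyses. On fat it says "The Resonance Health (HepaFat) scan will be used for liver fat and pancreatic fat"; Liver MultiScan supplies the LIF and cT1 scores, and AMRA supplies body composition. It does not mention visit labels, scan dates or reading order. It also lists a repeat MRI among the unscheduled visits, without a rule for when a scan is repeated.

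Section 3 makes all four imaging measures secondary change endpoints. Section 9.4.3 tests them as change from baseline within the single arm. Liver fat has more weight than its secondary rank suggests. It is part of the hypothesis in section 4.1 and of the primary objective in the synopsis, and section 4.2 says "ALT and hepatic steatosis have been selected as the two non-invasive biomarkers of response of NAFLD to gemcabene".

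**The concern.** Section 6.3 draws too wide a conclusion. Children, parents and investigators in an open-label trial know that the drug is being given. A vendor analysing a scan elsewhere need not know whether that scan came before or after twelve weeks of drug.

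This matters more here than in a randomized trial. With two arms, an analyst who knows the visit but not the arm would tend to shift both arms alike, and the shift would largely cancel in the comparison. With one arm, knowing the visit is knowing the treatment. A systematic difference in how Baseline and Week 12 scans are read, accepted or repeated cannot be separated from a drug effect.

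The interpretation of the imaging evidence is at stake, liver fat above all. The primary ALT analysis is not.

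**Working it through.** **Is there masking elsewhere in the plan?**
- Section 8.1 (imaging): vendors are named; nothing is said about masking or reading order.
- Section 10.1.3 (confidentiality): identity is replaced by a study number in data sent to the coordinating university. This does not hide the visit, and it does not describe image transfer to vendors.
- Section 10.1.6 (DSMB): summary safety and efficacy data at least quarterly; nothing on readers.
- Section 8.1 (central laboratory): samples are assayed only after all participants have finished their visits. No comparable step is stated for scans.

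The plan therefore allows readers to know the visit. It does not say that they do.

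**The plan's own figures.** Section 9.2 gives 36 completers, a 20% change with SD 40% (effect size 0.5), two-sided 0.05, a Wilcoxon test and 81% power. A one-sample noncentral t calculation with n = 36 gives 83.1%. With the Wilcoxon efficiency factor, the effective n is 36 × 3/π = 34.4, which gives 81.2%. A simulated signed-rank test gives 81.5%. Enrolment is 36/0.90 = 40. The figures reproduce. They concern ALT, and masking MRI reads changes none of them.

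**What an undetected shift would do (assumption only).** The documents give no figure for reader dependence. Suppose there is no true change, n = 36, and the test is a two-sided one-sample t-test at 0.05. Let reading alone shift the mean change by b standard deviations of the change. The noncentrality is b√36 = 6b.

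| Assumed b | 6b | False-positive rate |
|---|---|---|
| 0 | 0 | 5.0% |
| 0.05 | 0.3 | 6.0% |
| 0.1 | 0.6 | 9.0% |
| 0.2 | 1.2 | 21.5% |
| 0.3 | 1.8 | 41.7% |

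The table shows sensitivity. It does not estimate b, which could be close to zero.

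**Would codes alone mask the visit?** Section 5.5 expects 2–3 participants per site per month at 3 sites, so 6–9 per month (taken here as enrolled participants at a constant rate). Twelve weeks is 84/30.4 = 2.76 months. Before any on-schedule Week 12 scan, 6 × 2.76 ≈ 17 to 9 × 2.76 ≈ 25 of the 40 Baseline scans would arrive. Enrolment ends after 40/9 = 4.4 to 40/6 = 6.7 months, and every later scan is post-baseline. If scans are sent as acquired, arrival order gives away the visit.

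**How far do quarterly shuffled batches help?** Same assumptions, no dropout, months counted from the first Baseline visit:

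| Batch at month | Baseline scans (6/month; 9/month) | Week 12 scans (6/month; 9/month) |
|---|---|---|
| 3 | 6×3 = 18; 9×3 = 27 | 6×0.24 ≈ 1; 9×0.24 ≈ 2 |
| 6 | 6×3 = 18; 40−27 = 13 | 6×3 = 18; 9×3 = 27 |
| 9 | 40−36 = 4; 0 | 6×3 = 18; 40−(2+27) = 11 |

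The second batch is well mixed. The first is nearly all Baseline and the third nearly all post-baseline. Masking improves but stays partial.

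**Does anything need an early, labelled read?** Inclusion criterion 5c accepts a biopsy or an MRI from the past three years, and study MRI starts at Baseline, so entry does not depend on the study read. Section 8.2 says the "MRI liver fat result from baseline will be provided to each patient at the end of the study". Neither use requires the vendor to know the visit.

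**The case against.** The strongest reply is that the exposure is inferred from silence. Section 6.3 may only be explaining why treatment is not blinded, and section 8.1 does not describe what the vendors are sent. They may already work masked, or their outputs may be largely automatic. Section 2.1 describes the MRI methods as precise, and no section describes manual region placement or slice selection. This stands as a limit on what can be claimed. It does not remove the gap: precision does not exclude a systematic difference between visits, and a section headed as measures against bias should state how the scans are read.

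Four stronger readings are tempting, and the documents support none of them.
- A reader might infer that the vendors do know the visit, or that reads will be biased toward benefit. The plan permits the first and says nothing about the second.
- A reader might turn an assumed reading error into a relative change for a child at the 10% steatosis entry threshold. The documents give neither a reader-error figure nor an expected mean fat fraction, and the test is on the cohort, not on one child at the floor.
- A reader might infer that the trial's main analysis is compromised. The primary endpoint is ALT, a laboratory value assayed centrally in batch.
- A reader might infer that masking is nearly free. The documents contain no cost information, and MRI is scheduled at Baseline, Week 12, early termination and three long-term visits, for three vendors.

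It is also fair to object that vendor masking does not stop site staff from influencing which scans are repeated. That stands, and the repeat rule in the fix addresses it in part.

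**Conclusion.** The point holds as a low-severity improvement. The plan's stated reason for having no blinding does not extend to off-site image analysis, and no section masks the readers. In a single-arm pre/post design, any reader influence would pass undiluted into the change in liver fat, pancreatic fat, LIF/cT1 and body composition. The size of that influence is unknown and may be small; the false-positive table rests on assumed shifts. The arrival and batch counts rest on the accrual rate in section 5.5 being met evenly. Only secondary endpoints are affected, though liver fat is also in the hypothesis and the primary objective. Sample size, alpha and power stay as they are.

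**What to change.** In sections 6.3 and 8.1, state that dosing is open label but MRI analysis is masked:
- Each scan goes to the vendors under its own random code, with subject number, visit name and scan date removed from the label and image header. The data center holds the key.
- Scans are sent in shuffled batches that mix Baseline, Week 12 and later scans as far as accrual allows. Each batch is read in time for the quarterly DSMB review.
- Any request to repeat a scan on quality grounds comes from the vendor, under the code, before the fat result is released. A Baseline scan cannot usefully be repeated once dosing has begun, so this technical check should be made on receipt and kept apart from the batch measurement.

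If the vendors already read masked to visit and in random order, or their analysis involves no reader judgement, saying so in section 8.1 settles the matter.

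Cost: a code key must be kept, images must be relabelled before transfer, and reads wait for the next batch. The earliest batches will still be mostly Baseline scans, so masking is partial. A single shuffled read after the last Week 12 scan would mask more fully but would give the DSMB no imaging results during treatment; quarterly batches are the compromise. No extra reader, scan or visit is needed.
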